5.5.2 Secondary Analyses of Secondary Outcomes

As additional secondary analyses, we will perform a responder analysis which will repeat the analyses of the secondary anthropometric outcomes with the intervention group restricted to those participants who responded to the targeted prescribing pathway (i.e. had achieved $\geq 15\%$ weight loss at 52 weeks after randomisation). The purpose of these analyses is to compare the outcomes of “early and good” responders to the targeted prescribing pathway with those who received standard care only.

Therefore, all participants randomised to the standard care group will also be included in these responder analyses.

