2.2 Secondary Endpoints

2.2.1 Definition and Derivation of Secondary Endpoints

Endpoint	Time point (weeks)	Endpoint derivation
Anthropometric endpoint		
Absolute change in weight (kg) from baseline	16, 32, 52, 104	Follow-up weight – baseline weight
Relative change in weight (%) from baseline	16, 32, 52, 104	(Baseline weight – follow-up weight)/baseline weight * 100
Weight loss of $\geq 5\%$, $\geq 10\%$ and $\geq 15\%$	16, 32, 52, 104	Binary indicator of 1 if relative change in weight from baseline is $\geq 5\%$ loss (or $\geq 10\%$ or $\geq 15\%$, respectively), 0 otherwise
Maintenance of weight loss of $\geq 15\%$ among those who lost $\geq 15\%$ at 52 weeks	104	Binary indicator of 1 if relative change in weight from baseline is $\geq 15\%$ loss, 0 otherwise, only calculated for those who lost $\geq 15\%$ of baseline weight at 52 weeks.
Absolute change in BMI (kg/m^2) from baseline	52, 104	Follow-up BMI – baseline BMI
Absolute change in waist circumference (cm) from baseline	52, 104	Follow-up waist circumference – baseline waist circumference
Obesity-related co-morbidities and their treatments (General)		
Score on King's College Obesity Staging System assessment	52, 104	Scored as per Staging System (Appendix 1) as Stage 0 (normal health), 1 (at risk of disease), 2 (established disease), 3 (advanced disease) with baseline values also presented
Quality of life (EQ5D) – Descriptive System	52, 104	Scored as per https://www.unmc.edu/centric/_documents/EQ-5D-5L.pdf with change from baseline value analysed separately for each dimension
Quality of life (EQ5D) – Visual Analogue Scale	52, 104	Scored as per https://www.unmc.edu/centric/_documents/EQ-5D-5L.pdf with change from baseline value analysed
Impact of Weight on Quality of Life-Lite (IWQOL-Lite)	52, 104	Transformed total score on scale of 0-100 scored as per https://www.qualityoflifeconsulting.com/iwgol-lite.html with change from baseline

		value analysed
Patient Health Questionnaire-9 (PHQ-9)	52, 104	Scored as per Appendix 2 as minimal depression, mild depression, moderate depression, moderately severe depression, severe depression with baseline values also presented
Patient Health Questionnaire-9 (PHQ-9)	52, 104	Total score generated as per Appendix 2 with change from baseline analysed
Obesity-related co-morbidities and their treatments (Obstructive Sleep Apnoea; OSA)		

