3.3.4 Responder Population

The Responder population is defined as all participants in the intervention group who achieved $\geq 15\%$ weight loss at 52 weeks, and all participants in the standard care group. Participants will be analysed according to the treatment group to which they were randomised at baseline.

Participants who had bariatric surgery during the study period will be only be included at time-points prior to their bariatric surgery. They will be excluded from time-points after their bariatric surgery.

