5.5 Secondary Outcome Analyses

5.5.1 Primary Analysis of Secondary Outcomes

Secondary anthropometric outcomes will be analysed in a similar way to the primary analysis. These outcomes will be summarised overall and by treatment group.

Categorial outcomes will be summarised using count and percentage. Continuous outcomes will be summarised using mean, standard deviation, median, range, and interquartile range. Binary anthropometric outcomes will be compared between the two treatment arms using logistic regression models with the anthropometric outcome as the outcome and randomisation group and the stratification factors (site, baseline BMI) as covariates. The adjusted odds ratio will be presented along with 95% confidence interval and p-value comparing the two treatment arms. Continuous anthropometric outcomes will be compared using linear regression models with the anthropometric outcome as the outcome and randomisation group and the stratification factors (site, BMI) as covariates. The adjusted mean difference will be estimated along with 95% confidence interval and p-value comparing the two treatment arms. If continuous outcomes are non-normally distributed then they will be transformed or a more suitable regression model will be selected.

No formal statistical testing will take place for the other secondary outcomes due to the large amount of secondary outcomes and to reduce multiple testing. Instead, descriptive analyses will be performed to explore potential patterns in improvements. This will apply to the outcomes relating to obesity-related co-morbidities, referrals to Tier 4 services, treatment satisfaction, treatment compliance, and physical activity. Categorial outcomes will be summarised using count and percentage. Continuous outcomes will be summarised using mean, standard deviation, median, range, and interquartile range. Where it makes sense to do so, for continuous variables the baseline, follow-up, and change values will all be summarised; some outcomes can only be defined at follow-up and so this will not apply to those outcomes.

In all analyses, participants will be analysed in the group to which they were randomised at baseline. Only the complete cases population will be used for the secondary outcomes to reduce the number of models being fitted. Participants who have undergone bariatric surgery during the period of the study will be excluded from these analyses if their bariatric surgery took place before the analysed time-point.

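### The responder analysis selects only the intervention arm on week-52 weight loss: the week-52 contrasts are produced by the selection, and three planned odds ratios have no finite estimate

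*SAP*

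**What the plan says.** SAP 3.3.4 fixes the population: "The Responder population is defined as all participants in the intervention group who achieved" ≥15% loss at week 52, together with the entire standard-care arm. SAP 5.5.2 repeats the secondary anthropometric analyses "with the intervention group restricted to those participants who responded to the targeted prescribing pathway" and confirms that "all participants randomised to the standard care group will also be included in these responder analyses". Protocol 11.1 and 11.5 select in the same one-sided way. The only exclusion that touches controls concerns surgery: "They will be excluded from time-points after their bariatric surgery".

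The analyses repeated on this population are those of SAP 5.5.1. For binary outcomes, "The adjusted odds ratio will be presented along with 95% confidence interval and p-value comparing the two treatment arms". For continuous outcomes, "The adjusted mean difference will be estimated along with 95% confidence interval and p-value comparing the two treatment arms". The outcomes (SAP 2.2.1, Tables 16.8 and 16.9) include weight loss at week 52, the variable that defines selection. The SAP gives no caution about selection and no method for separation.

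Table 16.7, the template for the primary outcome, also has a Responder row. SAP 5.4.1 and 5.4.2 plan no such analysis. Both documents (Protocol 8.3.1.1, SAP 1.2.5) justify the 2:1 allocation by the need for enough responders, and both (Protocol 11.2, SAP 1.2.4) expect 40 of them.

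**The concern.** Intervention participants enter only if they did well on the outcome; controls enter however they did. Any between-arm difference therefore mixes a pathway effect with the effect of picking the best of one arm. At week 52 the outcome and the selection rule are the same measurement, so a difference is guaranteed whatever the drug does. At weeks 16, 32 and 104 a false difference remains to the extent that a person's weights correlate over time, and the model cannot separate it from a real effect.

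At stake are confidence intervals and p-values that would look like strong support for the pathway, with one row printed beside the primary result. SAP 1.2.1 gives the purpose of year 2 as comparing early, good responders with control; the one-sided week-104 contrasts cannot answer that.

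**Working it through.** **1. Models affected.** From SAP 2.2.1 and Tables 16.8 and 16.9:
- Continuous: weight in kg at 4 visits + weight in % at 4 + BMI at 2 + waist at 2 = 12.
- Binary: 3 thresholds × 4 visits + maintenance at week 104 = 13.
- Total 25. The maintenance endpoint is coded "0 otherwise, only calculated for those who lost" ≥15% at week 52, in both arms. Its responder run uses the same participants as the SAP 5.5.1 model and adds nothing. The other 24 carry the one-sided selection.

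**2. The plan's own figures.** The standard two-sided formula for 5% vs 16% at 2:1 and 80% power gives 96 + 192 = 288, and 288/0.75 = 384, close to the stated 392. Participants with data: 261 × 0.75 ≈ 196 and 131 × 0.75 ≈ 98, where power is 81.2%. For responders, 261 × 0.16 = 41.8, near the stated 40. That count omits the 25% drop-out assumed in the same paragraph. With it, 261 × 0.75 × 0.16 = 31.3; at the plan's 14% and 20% the result is 27.4 and 39.2.

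**3. Week 52, binary outcomes.** All responders meet ≥5%, ≥10% and ≥15%, so the intervention cell for no response is zero. Under the null with 5% responding, 196 × 0.05 ≈ 10 responders and 98 × 0.05 ≈ 5 control successes. Fitting 10/10 vs 5/98 with the group term:

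| Iterations | log-OR | SE | Wald p |
|---|---|---|---|
| 8 | 12.1 | 32 | 0.70 |
| 10 | 14.1 | 86 | 0.87 |
| 15 | 19.1 | 1043 | 0.985 |
| 25 | 29.1 | 150,000 | 1.00 |

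The estimate grows without limit. The same happens against 20/98 (≥10%) and 50/98 (≥5%).

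**4. Week 52, relative weight change, no effect.** Assume loss is normal with standard deviation SD and 5% reach 15%. The mean is then 15 − 1.645 × SD: 5.13 for SD 6 and 3.49 for SD 7. The mean among responders exceeds the overall mean by SD × φ(1.645)/0.05 = 2.063 × SD.
- SD 6: 12.38 points. SD 7: 14.44 points.
- In 4000 null trials per setting (196 vs 98, group + 5 sites + 2 BMI strata, covariates without effect), the planned linear model gave 12.38 and 14.41 points and p<0.05 in every trial.
- Controls reaching ≥5%: 51% (SD 6) or 41% (SD 7). Reaching ≥10%: 21% or 18%. Reaching ≥15%: 5%. Responders are at 100% on each.
- For SD 5 to 10 the gap is 10.3 to 20.6 points. If 16% of both arms responded, it is 7.6 to 15.2.

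Absolute weight and BMI change move with relative change; waist depends on its correlation with weight.

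**5. Other visits, no effect.** With the same mean and SD at the other visit, the false gap is about correlation × 2.063 × SD. Simulated with the planned linear model:

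| Correlation with week 52 | Gap, SD 6 | Gap, SD 7 | p<0.05 |
|---|---|---|---|
| 0.3 | 3.68 | 4.34 | 42% |
| 0.5 | 6.16 | 7.26 | 84–85% |
| 0.75 | 9.30 | 10.84 | 99% |

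For ≥15% at week 104 (SD 6.5, same correlations), 14%, 24% and 44% of responders qualify against 5% of controls. A logistic model with group only, counting non-estimable fits as no rejection, rejects in 22%, 50% and 87% of trials. With site and BMI stratum included, as the SAP requires, this falls to about 18–19%, 39–44% and 74–78%. The nominal rate is 5%.

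**The case against.** The strongest reply is that this is an additional secondary analysis, specified in the protocol, which claims no causal effect. SAP 5.4 names only the complete cases, ITT and per protocol analyses as showing effectiveness, and the plan already has a maintenance endpoint restricted in both arms. A lighter remedy would drop inference at week 52 only and label the other visits non-causal.

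This limits the severity but does not remove the defect. Adjusted estimates with confidence intervals and p-values are inference, and specifying them in advance does not undo selection on the outcome. The false differences at other visits are too large for a label to make the p-values readable.

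Several narrower points stand:
- The SAP does not say which test gives the p-value. For 10/10 vs 5/98 a likelihood-ratio test gives 2 × (43.52 − 19.75) = 47.5, p about 5 × 10⁻¹². The p-value is then tiny rather than near 1, but it reflects the selection; the odds ratio is still not finite.
- The SD, normality and correlations are not in the documents.
- A footnote to Table 16.8 marks ≥15% at week 52 as the primary analysis, so 24 of 25 could be read as 23 of 24.
- The maintenance model also conditions on post-randomisation response and expects only about 98 × 0.05 = 4.9 control responders.
- ≥15% loss at week 104 is a somewhat different question, since it counts people who first reach 15% in year 2.

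**Conclusion.** The concern holds, with high confidence, and should be fixed. Two results follow from the definition alone: the three week-52 odds ratios have no finite estimate, and the week-52 relative weight contrast is non-zero with no effect. Its size depends on the assumed SD and normality: 12.4 to 14.4 points for SD 6 to 7, with near-certain rejection. At other visits the bias depends on the assumed correlations, but its direction does not change for any positive correlation. These intervals and p-values cannot be read as a pathway effect. The primary analysis is unaffected. The expected count of 40 responders is a minor matter; about 31 (27 to 39) is consistent with the plan's own drop-out.

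**What to change.** 1. In SAP 5.5.2, report intervention responders descriptively, with no between-arm odds ratio, mean difference, confidence interval or p-value. Redefine the population in SAP 3.3.4 as intervention responders only and align the Responder row of Table 16.1.
2. Delete the Responder row from Table 16.7.
3. For lasting response between randomised arms, rely on ≥15% loss at 104 weeks in the complete cases population, already planned in SAP 2.2.1 and Table 16.8. The maintenance model stays in SAP 5.5.1, with a sentence saying that it compares groups selected after randomisation and that few control responders are expected.
4. Give the expected number of responders as about 31 (27 to 39) in a note to SAP 1.2.4, leaving the quoted protocol paragraph intact.
5. Record the departures from Protocol 11.1, 11.2 and 11.5 in SAP 5.8, and note there that the stated reason for 2:1 allocation now serves a descriptive summary.

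The cost is wording in a few SAP sections, two template rows and one entry in SAP 5.8. The SAP supplied is marked as a draft and allows amendment before database lock. The sponsor gives up the responder p-values, and one stated number becomes less favourable. Recruitment has closed, so the design does not change and no new data or models are needed. There are 25 fewer models, which suits the aim in SAP 5.5.1: "Only the complete cases population will be used for the secondary outcomes to reduce the number of models being fitted".

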5.5.3 Sensitivity Analyses

No sensitivity analyses are planned.

5.6 Subgroup Analyses

No subgroup analyses are planned.

5.7 Figures to be produced

Figure	Description
CONSORT diagram	See Section 5.1
Treatment flow	Based on figure in Section 1.2.1 with numbers added to show number of participants at each stage

5.8 Changes to the Planned Analysis

In the protocol, it stated that most secondary outcomes would be subject to formal statistical testing, with some secondary outcomes (safety, treatment compliance, treatment satisfaction) tabulated only, without statistical testing. However, due to the large number of secondary outcomes, it was decided that more secondary outcomes should be tabulated only to reduce the impact of multiple testing. The following outcomes were the ones for which the approach changed: obesity-related comorbidities, referrals to Tier 4 services, and physical activity.

In the protocol, the majority of the secondary outcomes were listed as absolute values, however the change from baseline will instead be analysed for continuous variables.

In the protocol, it states that ACR will be analysed as a secondary outcome for participants with diabetes. However, ACR was also measured for participants with prediabetes or hypertension and so these have been added to the ACR secondary outcome definition.

In the protocol, it was stated that participants who had bariatric surgery would be excluded from the complete cases, per protocol, and responder populations. However, it is more likely that these individuals will be poor responders and so excluding them could potentially bias the analyses. Therefore, participants who had bariatric surgery during the study period will be only be included at time-points prior to their bariatric surgery. They will be excluded from time-points after their bariatric surgery.

In the protocol, it stated that adjusted proportions or means would be presented by treatment group in the primary and secondary analyses. However, the unadjusted raw values are presented instead.

6 Safety and Adverse events (AEs)

The safety outcomes (including AEs and SAEs) will be summarised overall, by randomisation group, and by whether or not the participant was currently receiving LIRA 3mg treatment using count and percentage. The following information will also be presented:

- Incidence rate (per person-year) of each System Organ Class of AEs by treatment and overall
- Proportion of participants with at least one AE, by System Organ Class type, treatment arm, and overall
- Incidence rate (per person-year) of each expected AE type by treatment and overall
- Proportion of participants with at least one expected AE, by AE type, treatment arm, and overall
- Bar chart of number of AEs per individual, split by treatment
- Proportion of individuals with at least one AE of given severity by treatment and overall
- Proportion of individuals with at least one AE of given 'likelihood related' by treatment and overall.

For System Organ Classes with >0.1 AEs per person-year, the AEs broken down by higher level term.

Additionally, separate listings of all AEs and SAEs will be produced, including 'likelihood related', expectedness, duration, severity, action taken, outcome, and treatment, with sorting by randomisation group, participant ID, then date.

Finally, hypoglycaemia events will be tabulated by Glycaemic status for ADA and Novo Nordisk definition separately.

The safety analyses will use the safety population.

7 References

8 Appendix 1: Scoring for King's College Obesity Staging System

	Stage 0 Normal Health	Stage 1 At risk of disease	Stage 2 Established disease	Stage 3 Advanced disease
Airways	Normal	Snoring	CPAP therapy	Cor pulmonale
BMI	<35kg/m ²	35-40 kg/m ²	40-60 kg/m ²	>60 kg/m ²
Cardiovascular	<10% risk	10-20% risk	Heart disease	Heart failure
Diabetes	Normal	Impaired fasting glucose	Type 2 diabetes	Uncontrolled type 2 diabetes
Economic	Normal	Increased expense for clothes and travel	Workplace discrimination	Unemployment due to obesity
Functional	Can walk three flights of stairs	Can walk one or two flights of stairs	Requires mobility aid	Housebound
Gonadal	Normal	PCOS/erectile dysfunction	Subfertility	Sexual dysfunction leading to relationship breakdown
Health status (perceived)	Normal	Low mood or QoL	Depression or poor QoL	Severe depression
Image (body)	Normal	Dislikes body	Body image dysphoria	Eating disorder

Abbreviations: CPAP, Continuous Positive Airway Pressure; PCOS, Polycystic Ovarian Syndrome; QoL, Quality of Life.

9 Appendix 2: Scoring for PHQ-9 Questionnaire

PHQ-9* Questionnaire for Depression Scoring and Interpretation Guide

For physician use only

Scoring:

Count the number (#) of boxes checked in a column. Multiply that number by the value indicated below, then add the subtotal to produce a total score. The possible range is 0-27. Use the table below to interpret the PHQ-9 score.

Not at all	(#)	x 0 =	_____
Several days	(#)	x 1 =	_____
More than half the days	(#)	x 2 =	_____
Nearly every day	(#)	x 3 =	_____

Total score: _____

Interpreting PHQ-9 Scores

Diagnosis	Total Score	For Score	Action
Minimal depression	0-4	≤ 4	The score suggests the patient may not need depression treatment
Mild depression	5-9	5 - 14	Physician uses clinical judgment about treatment, based on patient's duration of symptoms and functional impairment
Moderate depression	10-14		
Moderately severe depression	15-19	> 14	Warrants treatment for depression, using antidepressant, psychotherapy and/or a combination of treatment.
Severe depression	20-27		

10 Appendix 3: Scoring for Epworth Sleepiness Scale

How Sleepy Are You?

How likely are you to doze off or fall asleep in the following situations? You should rate your chances of dozing off, not just feeling tired. Even if you have not done some of these things recently try to determine how they would have affected you.

For each situation, decide whether or not you would have:

- No chance of dozing =0
- Slight chance of dozing =1
- Moderate chance of dozing =2
- High chance of dozing =3

Write down the number corresponding to your choice in the right-hand column. Total your score below.

Situation Chance of Dozing

Sitting and reading .

Watching TV .

Sitting inactive in a public place (e.g., a theater or a meeting) .

As a passenger in a car for an hour without a break .

Lying down to rest in the afternoon when circumstances permit .

Sitting and talking to someone .

Sitting quietly after a lunch without alcohol .

In a car, while stopped for a few minutes in traffic .

Total Score = _____

Analyze Your Score

Interpretation:

≥10: Requires referral for sleep apnoea studies as indicates above average daily sleepiness.

11 Appendix 4: Scoring for Stop Bang Questionnaire

1.	Do you Snore loudly? Louder than talking or loud enough to be heard through a closed door	Yes	No
2.	Has anybody Observed you stop breathing during your sleep?	Yes	No
3.	Do you often feel Tired , fatigued, or sleepy during the daytime?	Yes	No
4.	High Blood Pressure? – do you have it or are you on treatment?	Yes	No
5.	Gender: Are you male or female?	M	F
6.	Is your Age above 50?	Yes	No

Clinic/nursing staff to complete:					
Neck Circumference – collar size		cm / inches	Neck circumference >40cm?	Yes	No
Weight		kg	-	-	-
Height		m	-	-	-
BMI		kg/m ²	BMI > 35 kg/m ²	Yes	No
Total STOP-BANG Score:				/ 8	

If the **STOP-BANG score is 5 or more**, consideration should be given to referral to the Sleep Service for investigation and treatment of possible Obstructive Sleep Apnoea (OSA).

- A score of 3 or more is sensitive for moderate-severe OSA but is not very specific, there is a high false positive rate.
- A score of 5-8 is far more specific and indicates a high probability of moderate-severe OSA.

12 Appendix 5: Definitions of hypoglycaemia

A hypoglycaemic episode will be defined as treatment emergent if the onset of the episode is on or after the first day of randomised treatment and no later than 14 days after the last day of randomised treatment. Hypoglycaemic events will be defined as nocturnal if the time onset is between 00:01 and 05:59 (both included).

A hypoglycaemic episode form and an Adverse Event (AE) form must be filled in for all hypoglycaemic episodes. Hypoglycaemic episodes requiring the assistance of another person to actively administer carbohydrate, glucagon, or other resuscitative actions (i.e., 'severe hypoglycaemic episodes') will be qualified as an event of special interest.

A different definition of hypoglycaemia will apply for patients with type 2 diabetes and a different definition will apply for patients without diabetes.

Classification of hypoglycaemia for participants with type 2 diabetes

All participants with diabetes will be supplied with a glucose meter and a diabetes diary for recording of hypoglycaemia, symptomatic episodes and routine blood glucose monitoring. Plasma glucose should always be measured from all participants with diabetes when there is the suspicion of a hypoglycaemic episode.

All plasma glucose values ≤ 3.1 mmol/L (56mg/dL), as well as values > 3.1 mmol/L (56mg/dL) when hypoglycaemic symptoms have occurred should be recorded by the participants in the diaries. Hypoglycaemic episodes will be recorded by the participant in his/her diary throughout the trial and must be transcribed into the CRF by the Investigator at each site visit throughout the trial.

Hypoglycaemic episodes will be summarised based on the American Diabetes Association (ADA) classification and Novo Nordisk's definition.

Novo Nordisk definition

In normal physiology, hypoglycaemia symptoms occur at a blood glucose level of approximately < 2.8 mmol/L (50 mg/dL)/plasma glucose level < 3.1 mmol/L (56 mg/dL). Therefore, Novo Nordisk has used this cut-off value to define minor hypoglycaemia.

Minor hypoglycaemic episode is defined as:

- An episode with symptoms consistent with hypoglycaemia with confirmation by plasma glucose < 3.1 mmol/L (56 mg/dL), or full blood glucose < 2.8 mmol/L (50 mg/dL) and which is handled by the subject himself/herself

- Or any asymptomatic plasma glucose value < 3.1 mmol/L (56 mg/dL) or full blood glucose value < 2.8 mmol/L (50 mg/dL). Minor hypoglycaemic episodes will be summarised according to this definition, and can be subject to additional analysis.

ADA hypoglycaemia classification

According to ADA the definition of a hypoglycaemic episode is categorised as:

Severe hypoglycaemia: An episode requiring assistance of another person to actively administer carbohydrate, glucagon, or other resuscitative actions.

Documented symptomatic hypoglycaemia: An episode during which typical symptoms of hypoglycaemia are accompanied by a measured plasma glucose concentration ≤ 3.9 mmol/L.

Asymptomatic hypoglycaemia: An episode not accompanied by typical symptoms of hypoglycaemia, but with a measured plasma glucose concentrations ≤ 3.9 mmol/L.

Probable symptomatic hypoglycaemia: An episode during which symptoms of hypoglycaemia are not accompanied by a plasma glucose determination (but that was presumably caused by a plasma glucose concentration ≤ 3.9 mmol/L).

Relative hypoglycaemia: An episode during which the participant reports any of the typical symptoms of hypoglycaemia and interprets those as indicative of hypoglycaemia, but with a measured plasma glucose concentration > 3.9 mmol/L.

Classification of hypoglycaemia for participants without diabetes

Participants without diabetes will not be routinely provided with blood glucose meters or diaries; hence blood glucose will not be measured in case of symptoms of hypoglycaemia unless it coincides with a clinic visit.

The hypoglycaemia events for participants without diabetes will be reported spontaneously i.e., symptoms of hypoglycaemia (not biochemically confirmed) occurring outside of visits to the clinic; severe hypoglycaemia will be defined as an episode requiring assistance of another person to actively administer carbohydrate, glucagon, or other resuscitative actions. In the event of severe or symptomatic hypoglycaemia patients will be given a glucose monitor and asked to record their blood glucose whenever they feel symptomatic.

13 Appendix 6: IPAQ scoring system

Further details including data processing rules can be found here:

<https://sites.google.com/site/theipaq/scoring-protocol>

Continuous Score

Data collected with the IPAQ long form can be reported as a continuous measure and reported as median MET-minutes. Median values and interquartile ranges can be computed for walking (W), moderate-intensity activities (M), and vigorous-intensity activities (V) within each domain using the formulas below. Total scores may also be calculated for walking (W), moderate-intensity activities (M), and vigorous-intensity activities (V); for each domain (work, transport, domestic and garden, and leisure) and for an overall grand total.

MET Values and Formula for Computation of MET-minutes

Work Domain

Walking MET-minutes/week at work = 3.3 * walking minutes * walking days at work

Moderate MET-minutes/week at work= 4.0 * moderate-intensity activity minutes * moderate-intensity days at work

Vigorous MET-minutes/week at work= 8.0 * vigorous-intensity activity minutes * vigorous-intensity days at work

Total Work MET-minutes/week =sum of Walking + Moderate + Vigorous MET-minutes/week scores at work.

Active Transportation Domain

Walking MET-minutes/week for transport = 3.3 * walking minutes * walking days for transportation

Cycle MET-minutes/week for transport= 6.0 * cycling minutes * cycle days for transportation

Total Transport MET-minutes/week = sum of Walking + Cycling MET-minutes/week scores for transportation.

Domestic and Garden [Yard Work] Domain

Vigorous MET-minutes/week yard chores= 5.5 * vigorous-intensity activity minutes * vigorous-intensity days doing yard work (Note: the MET value of 5.5 indicates that vigorous garden/yard work should be considered a moderate-intensity activity for scoring and computing total moderate intensity activities.)

Moderate MET-minutes/week yard chores= 4.0 * moderate-intensity activity minutes * moderateintensity days doing yard work

Moderate MET-minutes/week inside chores = 3.0* moderate-intensity activity minutes

* moderateintensity days doing inside chores.

Total Domestic and Garden MET-minutes/week =sum of Vigorous yard + Moderate yard + Moderate inside chores MET-minutes/week scores.

Leisure-Time Domain

Walking MET-minutes/week leisure = 3.3 * walking minutes * walking days in leisure

Moderate MET-minutes/week leisure = 4.0 * moderate-intensity activity minutes * moderate-intensity days in leisure

Vigorous MET-minutes/week leisure = 8.0 * vigorous-intensity activity minutes * vigorous-intensity days in leisure

Total Leisure-Time MET-minutes/week = sum of Walking + Moderate + Vigorous MET-minutes/week scores in leisure.

Total Scores for all Walking, Moderate and Vigorous Physical Activities

Total Walking MET-minutes/week = Walking MET-minutes/week (at Work + for Transport + in Leisure)

Total Moderate MET-minutes/week total = Moderate MET-minutes/week (at Work + Yard chores + inside chores + in Leisure time) + Cycling Met-minutes/week for Transport + Vigorous Yard chores MET-minutes/week

Total Vigorous MET-minutes/week = Vigorous MET-minutes/week (at Work + in Leisure)

Note: Cycling MET value and Vigorous garden/yard work MET value fall within the coding range of moderate-intensity activities.

Total Physical Activity Scores

An overall total physical activity MET-minutes/week score can be computed as: Total physical activity MET-minutes/week = sum of Total (Walking + Moderate + Vigorous) METminutes/week scores.

This is equivalent to computing: Total physical activity MET-minutes/week = sum of Total Work + Total Transport + Total Domestic and Garden + Total Leisure-Time MET-minutes/week scores.

As there are no established thresholds for presenting MET-minutes, the IPAQ Research Committee proposes that these data are reported as comparisons of median values and interquartile ranges for different populations.

14 Appendix 7 Definitions for adherence of participants with the LIRA 3mg

Individuals that didn't receive 70% of the doses as determined by the protocol (i.e. in the first 16 weeks or there after whilst continuing to meet the continue rules of the protocolised treatment schedule) will be classed as not adhering with the LIRA 3mg pathway.

Defining days taking LIRA

The number of days taking LIRA will be calculated as the time from first dose dispensed (normally at baseline visit) to the last known date of individuals taking the LIRA. Where individuals are recorded as not completing the trial due to stopping the LIRA, the date of last dose of LIRA in the completion form will be used; if this is not recorded then the date of first visit at which individuals say they are not happy to continue taking LIRA will be used; and where neither of these are recorded the date of the last visit that individuals said they are happy to continue LIRA will be used.

14.1 52 weeks

Individuals will then be assessed for whether they have received 70% as per table below.

Stopping rule on protocolised treatment schedule	Did not receive 70% of planned doses	Did receive 70% of planned doses
Did not meet rule to continue on Lira at 16 weeks (either <5% weight loss or not measured)	If days taking LIRA is <70% of days between baseline and Week 16. Or, if Week 16 date missing, if days taking LIRA is ≤ 78 .	If days taking LIRA is $\geq 70\%$ of days between baseline and Week 16. Or, if Week 16 date missing, if days taking LIRA is >78
Did meet rule to continue Lira ($\geq 5\%$ weight loss) at 16 weeks but did not meet rule to continue Lira at 32 weeks (either <10% weight loss or not measured)	If days taking LIRA is <70% of days between baseline and Week 32. Or, if Week 32 date missing, if days taking LIRA is ≤ 156 .	If days taking LIRA is $\geq 70\%$ of days between baseline and Week 32. Or, if Week 32 date missing, if days taking LIRA is >156 .
Did meet rule to continue Lira ($\geq 5\%$ weight loss) at 16 weeks and did not meet rule to continue Lira at 32 weeks ($\geq 10\%$ weight loss)	If days taking LIRA is <70% of days between baseline and week 52. Or, if week 52 date missing, if days taking LIRA is ≤ 254 .	If days taking LIRA is $\geq 70\%$ of days between baseline and week 52. Or, if week 52 date is missing, if days taking LIRA is >254 .

14.2 104 weeks

Individuals will then be assessed for whether they have received 70% as per table below.

Stopping rule on protocolised treatment schedule	Did not receive 70% of planned doses	Did receive 70% of planned doses
Did not meet rule to continue on Lira at 16 weeks (either <5% weight loss or not measured)	If days taking LIRA is <70% of days between baseline and Week 16. Or, if Week 16 date missing, if days taking LIRA is ≤ 78 .	If days taking LIRA is $\geq 70\%$ of days between baseline and Week 16. Or, if Week 16 date missing, if days taking LIRA is >78
Did meet rule to continue Lira ($\geq 5\%$ weight loss) at 16 weeks but did not meet rule to continue Lira at 32 weeks (either <10% weight loss or not measured)	If days taking LIRA is <70% of days between baseline and Week 32. Or, if Week 32 date missing, if days taking LIRA is ≤ 156 .	If days taking LIRA is $\geq 70\%$ of days between baseline and Week 32. Or, if Week 32 date missing, if days taking LIRA is >156 .
Did meet rule to continue Lira ($\geq 5\%$ weight loss) at 16 weeks, did meet rule to continue Lira at 32 weeks ($\geq 10\%$ weight loss) and did not meet rule to continue Lira at 52 weeks (either <15% weight loss or not measured)	If days taking LIRA is <70% of days between baseline and week 52. Or, if Week 52 date missing, if days taking LIRA is ≤ 254 .	If days taking LIRA is $\geq 70\%$ of days between baseline and week 52. Or, if Week 52 date missing, if days taking LIRA is >254 .
Did meet rule to continue Lira ($\geq 5\%$ weight loss) at 16 weeks, did meet rule to continue Lira at 32 weeks ($\geq 10\%$ weight loss) and did meet rule to continue Lira at 52 weeks ($\geq 15\%$ weight loss)	If days taking LIRA is <70% of days between baseline and week 104. Or, if Week 104 date missing, if days taking LIRA is ≤ 510 .	If days taking LIRA is $\geq 70\%$ of days between baseline and week 104. Or, if Week 104 date missing, if days taking LIRA is >510 .

15 Appendix 8: Baseline and follow-up Glycaemic Status Definitions

